8.0 CRITERIA FOR REMOVAL FROM PROTOCOL THERAPY AND OFF STUDY CRITERIA

8.1 Criteria for Removal from Protocol Therapy

- a) Progressive disease.
- b) Refusal of further protocol therapy by patient/parent/guardian.
- c) Completion of planned therapy.
- d) Physician determines it is in patient's best interest.
- e) Unacceptable toxicity due to protocol therapy or delays in therapy that meet the criteria in [Section 5.0](#).
- f) Development of a second malignancy.
- g) Repeat eligibility studies (if required) prior to the initiation of protocol therapy are outside the parameters required for eligibility (see [Section 3.2](#)).
- h) Pregnancy

Patients who are off protocol therapy are to be followed until they meet the criteria for Off Study (see below). Follow-up data will be required unless patient is taken off study.

8.2 Off Study Criteria

- a) Death.
- b) Lost to follow-up.
- c) Patient enrollment onto another COG anti-cancer therapeutic study (e.g., at recurrence).
- d) Withdrawal of consent for any further data submission.
- e) Fifth anniversary of the date the patient was enrolled on this study.
- f) Patient never received protocol therapy.

[figure not shown]

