3.0 STUDY ENROLLMENT PROCEDURES AND PATIENT ELIGIBILITY

3.1 Study Enrollment

3.1.1 Patient Registration

Prior to enrollment on this study, patients must be assigned a COG patient ID number. This number is obtained via the Patient Registry module in OPEN once authorization for the release of protected health information (PHI) has been obtained. The COG patient ID number is used to identify the patient in all future interactions with COG. If you have problems with the registration, please refer to the online help. For additional help or information, please contact the CTSU Help Desk at [name] or [contact].

In order for an institution to maintain COG membership requirements, every patient with a known or suspected neoplasm needs to be offered participation in APEC14B1, *Project:EveryChild A Registry, Eligibility Screening, Biology and Outcome Study*.

A Biopathology Center (BPC) number will be assigned as part of the registration process. Each patient will be assigned only one BPC number per COG Patient ID. For additional information about the labeling of specimens please refer to the Pathology and/or Biology Guidelines in this protocol.

Please see [Appendix I](#) for detailed CTEP Registration Procedures for Investigators and Associates, and Cancer Trials Support Unit (CTSU) Registration Procedures including: how to download site registration documents; requirements for site

registration, submission of regulatory documents and how to check your site's registration status.

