7.1 End of Therapy & Follow-up

STUDIES TO BE OBTAINED	End of Therapy ¹	Time from End of Therapy (Months)													At Relapse
		3	6	9	12	15	18	24	30	36	42	48	54	60	
History	X	X	X	X	X	X	X	X	X	X	X	X	X	X	X
Physical Exam with VS (including BP)	X	X	X	X	X	X	X	X	X	X	X	X	X	X	X
Ht, Wt, BSA	X	X	X	X	X	X	X	X	X	X	X	X	X	X	X
CBC, differential, platelets	X	X	X	X	X		X	X		X		X		X	
Electrolytes including Ca ⁺⁺ , PO ₄ , Mg ⁺⁺	X	X	X	X	X		X	X		X		X		X	
Creatinine, ALT, bilirubin	X	X	X	X	X		X	X		X		X		X	
ECHO	X				X			X		X		X		X	
Cross sectional imaging of primary tumor site (MRI or CT)	X		X		X		X	X		X					X
¹²³ I-MIBG scan ²	X	X	X		X		X	X		X					X
FDG-PET scan ²	X	X	X		X		X	X		X					X
Bilateral bone marrow aspirates and biopsies	X														X
Biologic correlative studies (see Section 14.0 & Appendix X)	X														X

¹Obtain within 2 weeks of completing Cycle 6, or Cycle 5 for patients that discontinue isotretinoin.

²FDG-PET only in patients with MIBG non-avid disease at diagnosis who are followed by FDG-PET in place of ¹²³I-MIBG scan.

Note: If enrolled in APEC14B1/ANBL00B1 and consented to optional cell banking, submit PB and BM specimens if relapse occurs.

See COG Late Effects Guidelines for recommended post treatment follow-up:
<http://www-survivorshipguidelines.org/>

Note: Follow-up data are expected to be submitted per the Case Report Forms (CRFs) schedule.

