9.3.2 Secondary Endpoints

For event-free survival, time to event will be calculated from the time of start of protocol therapy to the occurrence of disease relapse or progression, secondary malignancy, or death. For overall survival, death will be the only event considered and time to death will be calculated from the time of start of protocol therapy. Patients without an event or death will be censored at the time of last follow-up.

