9.3.4 Assessment of Study Objectives

The primary study objective ([Aim 1.1.1](#)) related to feasibility will be assessed by estimation of the feasibility therapy completion rate together with a 95% Wilson CI. The therapy will be deemed feasible if the 95% CI placed on the percentage of patients that complete at least 5 cycles of dinutuximab + chemotherapy without PD within 30 weeks contains 75% and the interim monitoring rules for feasibility and excessive toxicity ([Section 9.3.3](#)) are not triggered.

To address Secondary [Aim 1.2.1](#), adverse events (Grade ≥ 3) experienced by patients evaluable for toxicity will be descriptively summarized.

To assess Secondary [Aim 1.2.2](#), EFS and OS Kaplan-Meier curves and estimates will be generated.

Exploratory [Aim 1.3.1](#) will be assessed by a descriptive comparison of adverse events (Grade ≥ 3) experienced by patients evaluable for toxicity according to prior anti-GD2 directed therapy (yes vs. no) status.

To address Exploratory [Aim 1.3.2](#), response will be assessed by the revised INRC²⁸ and descriptively summarized among those evaluable for response (see [Section 9.4](#)).

To address Exploratory [Aim 1.3.3](#), immune and cytokine profiles will be described at baseline and the change in immune and cytokine profiles from baseline will be descriptively summarized. There will be a descriptive comparison of the immune and cytokine profiles of those receiving chemo-immunotherapy on this pilot in the frontline setting and those receiving chemo-immunotherapy (Arm A) in the relapsed/refractory setting on ANBL1821. There will also be a descriptive comparison of immune profiles at the start and end of Post-Consolidation therapy between those who receive chemo-immunotherapy on this pilot versus standard immunotherapy on ANBL1531 (Arm A) to assess the impact of these regimens on immune reconstitution.

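### Joining another COG trial at recurrence ends required follow-up, so the descriptive overall survival estimate can be too high unless later survival dates are obtained

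*Combined protocol and SAP*

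**What the plan says.** Four provisions of the combined protocol and SAP act together.

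- Section 8.2(c) lists as an off-study event: "Patient enrollment onto another COG anti-cancer therapeutic study (e.g., at recurrence". Recurrence is the protocol's own example.
- Section 8.1 keeps patients who stop protocol therapy under follow-up only until an off-study criterion is met: "Follow-up data will be required unless patient is taken off study".
- Section 9.3.2 counts only death as an OS event, timed from the start of protocol therapy, and adds: "Patients without an event or death will be censored at the time of last follow-up".
- Section 9.3.4 gives the whole analysis for Aim 1.2.2: "EFS and OS Kaplan-Meier curves and estimates will be generated". It plans no sensitivity analysis and no count by reason for censoring.

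Three other places bear on whether later survival could still be known.

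- Section 3.1.1 says "every patient with a known or suspected neoplasm needs to be offered participation in APEC14B1", which its title describes as including an outcome study, and that "The COG patient ID number is used to identify the patient in all future interactions with COG".
- Section 7.1 mentions that registry at relapse only for specimens: "If enrolled in APEC14B1/ANBL00B1 and consented to optional cell banking, submit PB and BM specimens if relapse occurs".
- Sections 9.3.1 and 9.3.3.1 use COG data on 108 patients randomized on ANBL0532 and then enrolled on ANBL0032.

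Follow-up otherwise ends at the fifth anniversary of enrolment (8.2(e)).

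**The concern.** Kaplan-Meier treats a censored patient as having the same later risk of death as those still being followed. A patient who leaves at recurrence does not. The abstract and section 2.1 say that 25-35% recur and that their long-term survival is dismal. Such patients contribute survival time up to recurrence, while their later deaths are not required to be reported. The error runs upward, in the regimen's favour.

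The route is realistic. Section 2.5 names a COG Phase 2 study, ANBL1821, for first relapse or refractory disease, although the documents do not say whether patients from this trial could join it.

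What is at stake is the reporting of one secondary aim. A reader may well set this OS beside the 2-year COG figures in section 2.2, and the planned analysis would not say how many patients were censored for this reason.

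**Working it through.** **No plan figure to reproduce.** The documents give no OS target, precision or expected number of deaths. The sample size of 40 does check: √(0.25/40) = 0.0791, the maximum standard error stated in section 9.1.

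**Inputs.**

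- From the protocol: a recurrence share of 25-35%, with no time point given, and 40 patients.
- Assumed: recurrence accrues at a constant rate over 3 years and then stops; median survival after relapse is 1 or 2 years (exponential); no deaths occur without relapse; a share q of relapsed patients (10%, 25% or 50%) joins another COG trial; no later survival dates are recovered.

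**Model, up to 3 years.** Let p be the recurrence share and m the median survival after relapse.

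- Relapse hazard λ = −ln(1−p)/3; death hazard after relapse μ = ln 2/m.
- Event-free: S₀(t) = e^(−λt).
- Relapsed and alive: R(t) = λ/(μ−λ) × (e^(−λt) − e^(−μt)).
- True OS = S₀(t) + R(t).
- Large-sample Kaplan-Meier with joiners censored at relapse = exp{−∫₀ᵗ μ(1−q)R(u) / [S₀(u) + (1−q)R(u)] du}.

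**Worked case: p = 35%, m = 1 year, q = 50%, at 2 years.**

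- λ = 0.1436, μ = 0.6931.
- S₀(2) = 0.7504.
- R(2) = 0.2613 × (0.7504 − 0.2500) = 0.1307.
- True OS = 88.1%. Kaplan-Meier = 93.5%. Overstatement = 5.4 points.

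**Overstatement at 2 years, in points:**

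| Recurrence by 3 years | Median after relapse | q = 10% | q = 25% | q = 50% |
|---|---|---|---|---|
| 25% | 2 years | 0.45 | 1.14 | 2.35 |
| 25% | 1 year | 0.74 | 1.87 | 3.86 |
| 35% | 2 years | 0.61 | 1.57 | 3.29 |
| 35% | 1 year | 1.01 | 2.59 | 5.41 |

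In a milder form, enrolment comes 1 month after relapse and joiners have half the death hazard. The range is then 0.20 to 2.67 points, so both forms together span about 0.2 to 5.4.

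**Scale.** One binomial standard error with 40 patients is √(0.95×0.05/40) = 3.4 points at 95% OS and √(0.88×0.12/40) = 5.1 points at 88%. In the base form the number censored under 8.2(c) by 2 years is 40 × q × (1 − S₀(2)). This runs from 40 × 0.10 × 0.175 = 0.7 to 40 × 0.50 × 0.250 = 5.0 patients.

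**Cross-check with the protocol's historical figures.** Calibrating instead to the 2-year EFS of 66% and OS of 86% in section 2.2 gives μ = 0.54 per year. Kaplan-Meier is then 88.9% at q = 25% and 92.1% at q = 50%, an overstatement of 2.9 and 6.1 points. The standard error at 86% is √(0.86×0.14/40) = 5.5 points. The direction is the same and the size similar, slightly above the table's top value. At q = 75% it would be 95.8 − 86.0 = 9.8 points, so about one standard error is a fair ceiling only for shares up to half.

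**Later times.** With the same assumptions the 5-year overstatement is 1.4 to 13.2 points in the base form and 0.8 to 9.0 in the milder form.

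**The case against.** The strongest reply is that the dates will probably be available. The trigger is enrolment on another COG study, so a later death would be known to the same group under the same patient ID. COG has already followed patients from ANBL0532 into ANBL0032 for the benchmarks in 9.3.1 and 9.3.3.1. Section 9.3.2 censors at last follow-up, not at the off-study date, so a later date could be used if obtained. Section 7.1 also refers to a case report form schedule that was not available here, nor were the consent pages. Either might settle whether vital status continues.

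Much of this stands. It makes loss of the dates uncertain and a remedy cheap. A reader might infer that OS is necessarily cut off at recurrence for every patient who joins; the documents do not support that. They also do not provide the opposite assurance. The ANBL0532 to ANBL0032 link shows that linkage is possible, not that it is planned for this OS analysis. APEC14B1 need only be offered, and its one instruction at relapse concerns specimens.

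The second reply is that OS is descriptive, in about 40 patients, with no comparator, test or threshold. That stands in full and limits the point to reporting.

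**Conclusion.** As written, 8.1, 8.2(c) and 9.3.2 together permit informative censoring at recurrence, and the Kaplan-Meier OS can be overstated. This is a minor point worth correcting.

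The size is not known. It is zero if nobody joins another COG trial or if later dates are recovered. With 10-50% of relapsed patients joining and no dates recovered, it is about 0.2 to 5.4 points at 2 years, at most about one standard error with 40 patients. Only the recurrence share and sample size come from the protocol.

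Two stronger readings should be resisted.

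- A reader might take the largest 5-year value, 13.2 points, as the expected error. It needs 35% recurrence, a 1-year median, half of relapsed patients joining at once and no recovered dates. The plan names no OS time point.
- A reader might conclude that the trial's result is compromised. It is not. Disease progression during protocol therapy already counts against feasibility, the monitoring rules do not use OS, and recurrence is itself an EFS event that occurs before the patient leaves.

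**What to change.** State in 8.2 and 9.3.2 that enrolment on another COG study does not end vital-status follow-up for OS. Take the date of death or last-known-alive, up to the fifth anniversary, from the later COG study or APEC14B1 through the COG patient ID. This should be subject to consent and to 8.2(d), "Withdrawal of consent for any further data submission". Report beside the OS curve the number of patients still censored under 8.2(c).

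The cost is a sentence in each section, a small cross-study data link, a check of the consent wording on vital status and one reported count. If linkage is already routine, the sentences alone settle the matter.

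An analysis counting these patients as deaths on leaving is not recommended. In the model above it lies further from the truth than Kaplan-Meier in every 2-year scenario. In the worked case, with truth at 88.1%, it gives 81.6% (6.5 points low) against 93.5% (5.4 points high). It can also be worse at 5 years. In the milder form with 35% recurrence, a 2-year median and half joining, the truth is 79.6%, Kaplan-Meier 85.2% and this analysis 70.3%.

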9.0 STATISTICAL CONSIDERATIONS

9.1 Sample Size and Study Duration

Forty eligible and evaluable patients will be necessary to analyze the primary objective, assessing the feasibility of dinutuximab, GM-CSF, and isotretinoin administration in combination with irinotecan and temozolomide during Post-Consolidation for patients with prior tandem ASCT. Enrollment of up to 45 patients will be required in order to generate the 40 eligible and evaluable patients that will be analyzed for the feasibility primary objective, accounting for potential ineligible patients. With 40 eligible and evaluable patients with prior tandem ASCT, the estimate of feasibility will have a standard error of at most 0.0791.

Approximately 223 patients/year enrolled on ANBL00B1 have high-risk neuroblastoma. Estimated accrual on high-risk neuroblastoma frontline therapeutic trials ANBL1531 and ANBL17P1 is 163 patients/year and 29 patients/year, respectively. Therefore, approximately 31 patients/year with high-risk neuroblastoma will not enroll on a frontline therapeutic trial and will be potentially eligible for the proposed study ([Figure 1](#)). Of the patients enrolled on ANBL1531 (163 patients/year), 124 patients/year are expected to be eligible for randomization and, if they proceed with randomization, will not be eligible for this study. Patients assigned to a treatment arm and not eligible for randomization (i.e., patients with MIBG non-avid disease [Arm D] or tumors demonstrating an ALK aberration [Arm E]) will also not be eligible for our pilot study. We predict that 15% of those eligible for randomization on ANBL1531 will refuse randomization and will be eligible for the proposed study (19 patients/year). Therefore, we anticipate that approximately 50 patients/year will be potentially eligible to enroll on ANBL19P1. If we assume 50-60% of the potentially eligible patients choose to enroll on this study and meet eligibility criteria, our expected accrual is 25-30 patients/year.

We estimate an accrual duration of approximately 1.5-2 years and an additional 6 months for completion of therapy and feasibility evaluation, for a total study duration of approximately 2.5 years.

Figure 1. Accrual Diagram

9.2 Study Design

This trial is a prospective, single arm pilot study to assess the feasibility of administering dinutuximab in combination with irinotecan, temozolomide, and GM-CSF in the frontline, Post-Consolidation setting in patients with high-risk neuroblastoma who have received prior tandem transplant. All patients will receive the same treatment on this trial. A stopping rule for feasibility will be used to monitor patients for early indication of inability to successfully administer all intended cycles of therapy. In addition, patients will be monitored for the occurrence of excessive toxicities.

9.3 Methods of Analysis

9.3.1 Primary Endpoint

The primary objective of the study is to determine the feasibility of administering 5 cycles of dinutuximab + GM-CSF and isotretinoin in combination with chemotherapy (irinotecan and temozolomide) in patients with high-risk neuroblastoma in the front-line setting following Consolidation with tandem transplant. In the absence of treatment delays, each cycle of dinutuximab-containing therapy will be completed in approximately 4 weeks, and there are 5 cycles of dinutuximab/chemotherapy-containing therapy included on this trial. Patients with disease progression detected at any time during protocol therapy or who meet pre-specified toxicity criteria will discontinue protocol-specified treatment and count against the feasibility of protocol therapy. The primary endpoint is the proportion of patients who complete 5 cycles of dinutuximab + chemotherapy without progressive disease within 30 weeks from the date of first treatment among patients who start protocol therapy.

Of the 108 patients randomized to tandem transplant on ANBL0532 that enrolled on ANBL0032 after randomization was halted, 87 (80.6%) completed at least 5 cycles of dinutuximab without progressive disease within 30 weeks. A feasibility therapy completion rate of 75% will be targeted on this study. With a sample size of 40 eligible and evaluable patients, at the 5% significance level, there will be

80% and 90% power, respectively, to detect a reduction in the therapy completion rate from target of 75% to 55.0% and 51.5%. This therapy will be declared feasible if a 95% Wilson confidence interval (CI) placed on the percentage of patients that complete at least 5 cycles of dinutuximab + chemotherapy without PD within 30 weeks contains 75% and the interim monitoring rules for feasibility and excessive toxicity (see [Section 9.3.3](#)) are not triggered. Using the closed-form formula for a 95% Wilson CI and resolving, the probability of this CI covering the value 75% when the true feasibility therapy completion rate is 50% or 60% is 0.0769 and 0.4402, respectively.

Patients who have dose modifications but remain on therapy and are able to complete the 5 cycles without PD within 30 weeks will not count against feasibility. Patients who meet off protocol criteria due to toxicity (i.e., require greater than one dose modification for irinotecan or temozolomide, or meet off protocol criteria for dinutuximab per [Section 5.0](#)) or other criteria for removal from protocol therapy (see [Section 8.1](#)) before completion of 5 cycles will count against feasibility. Any eligible patient with prior tandem ASCT who receives at least one dose of protocol therapy will be considered evaluable for the primary endpoint.

Note: Discontinuation of isotretinoin will not count against the feasibility endpoint on this study.

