9.3.3.1 Feasibility

We will monitor for early indication of inability to administer all 5 intended cycles of dinutuximab + chemotherapy without PD within 30 weeks. Of the 108 patients randomized to tandem transplant on ANBL0532 that enrolled on ANBL0032 after randomization was halted, 89 (82.4%) completed at least 3 cycles of dinutuximab without progressive disease within 18 weeks. This feasibility monitoring rule will monitor that $\geq 75\%$ of patients will complete at least 3 cycles of dinutuximab + chemotherapy without PD within 18 weeks among patients who start protocol therapy. Patients who have dose modifications but remain on therapy and are able to complete the cycles without PD within the specified time frame above will not count against the feasibility monitoring rule.

A one-sided Pocock group-sequential boundary with a sample size of 40 will be used to monitor the number of patients that fail to receive at least 3 cycles of chemo-immunotherapy without progressive disease within

18 weeks. Interim monitoring will be done after 1/4 and 1/2 of patients have been evaluated for completion of at least 3 cycles of protocol therapy without PD (Table 3). The upper bound on the number of patients not receiving at least 3 cycles of protocol therapy without PD within 18 weeks that are needed to declare the therapy not feasible uses a cumulative alpha level of 0.125. The probability of declaring the regimen not feasible under the alternative hypothesis non-completion rates of 45% and 50% appears in Table 4. The average sample size when the non-completion rate is 25%, 45%, and 50% is 38.00, 25.32, and 20.86, respectively.

Table 3. Interim monitoring plan and number of observed patients that do not complete at least 3 cycles of chemo-immunotherapy without PD within 18 weeks needed to declare therapy not feasible.

Monitoring percent of total information	Number of patients evaluated for therapy completion	Monitoring boundary	Number of observed non-completions to declare not feasible
25%	10	1.6989 (p=0.04467)	≥ 6 (60%)
50%	20	1.6276 (p=0.05180)	≥ 9 (45%)

Table 4. Probability of detecting regimen not feasible under various alternative hypothesis therapy non-completion rates.

Monitoring percent of total information	Number of patients evaluated for therapy completion	Power under a true non-completion rate of 45%	Power under a true non-completion rate of 50%
25%	10	0.2616	0.3770
50%	20	0.5857	0.7483

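### The primary feasibility rule requires the 95% Wilson interval to contain 75%, so it gives no conclusion for 36-40 completions out of 40

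*Combined protocol and SAP*

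**What the plan says.** Section 9.3.1 sets the decision rule for the primary endpoint: "This therapy will be declared feasible if a 95% Wilson confidence interval (CI) placed on the percentage of patients" completing at least 5 cycles "without PD within 30 weeks contains 75% and the interim monitoring rules for feasibility and excessive toxicity" are not triggered. Section 9.3.4 repeats the condition when it assesses Aim 1.1.1: "chemotherapy without PD within 30 weeks contains 75% and the interim monitoring rules for feasibility and excessive toxicity" again appear together. Neither section says what is concluded when the whole interval lies above 75%, and no other section does.

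The related text looks only downward:

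- Section 9.3.1 gives power "to detect a reduction in the therapy completion rate from target of 75% to 55.0% and 51.5" percent.
- Section 9.3.1 reports "the probability of this CI covering the value 75% when the true feasibility therapy completion rate is 50% or 60" percent, as 0.0769 and 0.4402. No probability is given for a true rate at or above 75%.
- Section 9.2 describes the feasibility stopping rule as a watch for "early indication of inability to successfully administer all intended cycles of therapy".
- Section 9.3.3.1 uses a one-sided boundary on patients who fail to complete. Its 3-cycle standard is that at least 75% "of patients will complete at least 3 cycles of dinutuximab + chemotherapy without PD within 18 weeks among patients who start protocol therapy".

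The reference rate in Section 9.3.1 comes from 108 earlier tandem-transplant patients, of whom "87 (80.6%) completed at least 5 cycles of dinutuximab without progressive disease within 30 weeks".

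**The concern.** An interval can fail to contain 75% in two ways. If it lies below 75%, too few patients completed, and withholding the declaration is what the design intends. If it lies above 75%, completion was better than the target, yet the written condition fails in the same way.

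If the rule's *if* is read as *only if*, the rule denies feasibility to the best results. If it is read as a sufficient condition only, the rule is silent on them. Either way the analyst who sees 36 or more completions has no prespecified conclusion. They must withhold the declaration or choose a conclusion after seeing the data. This is the go/no-go rule for the only primary aim, and Section 2.1 makes the case for later trials conditional on feasibility being shown.

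The two-sided 5% level is not at issue. Only the conclusion for the upper side is missing.

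**Working it through.** **Inputs.** n = 40 evaluable patients (Sections 9.1 and 9.3.1); target 75%, 95% Wilson interval and historical rate 87/108 = 80.6% (Section 9.3.1); 3-cycle historical rate 89/108 and Table 3 (Section 9.3.3.1); Table 5 (Section 9.3.3.2).

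**Which results meet the condition.** With p̂ = x/n and z = 1.96, the Wilson limits are

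[p̂ + z²/(2n) ± z·√(p̂(1−p̂)/n + z²/(4n²))] / (1 + z²/n).

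| Completions of 40 | 95% Wilson interval | 75% is |
|---|---|---|
| 24 | 0.446 to 0.737 | above the interval |
| 25 | 0.470 to 0.758 | inside |
| 35 | 0.739 to 0.945 | inside |
| 36 | 0.769 to 0.960 | below the interval |
| 38 | 0.835 to 0.986 | below the interval |
| 40 | 0.912 to 1.000 | below the interval |

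Cross-check: the Wilson interval contains 0.75 exactly when |p̂ − 0.75| ≤ 1.96·√(0.75 × 0.25/40) = 1.96 × 0.0685 = 0.134. So p̂ must lie between 0.616 and 0.884, and x between 24.6 and 35.4. The condition therefore holds for x = 25 to 35 only.

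**Reproducing the plan's figures.** The exact binomial P(25 ≤ X ≤ 35) is 0.0769 at a true rate of 50% and 0.4402 at 60%, which matches Section 9.3.1. P(X ≥ 25), with no upper cutoff, is also 0.0769 and 0.4402 to four decimals.

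**Interval condition alone, n = 40.**

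| True completion rate | 24 or fewer | 25 to 35 (condition met) | 36 or more (no conclusion) |
|---|---|---|---|
| 75% | 0.0262 | 0.9577 | 0.0160 |
| 87/108 | 0.0022 | 0.9092 | 0.0886 |
| 85% | 0.0001 | 0.7366 | 0.2633 |
| 90% | 0.0000 | 0.3710 | 0.6290 |

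The chance of meeting the written condition falls as true completion rises above the target. At 87/108 the condition is missed through high completion about 40 times as often as through low completion (0.0886/0.0022).

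**Other evaluable numbers.** For n from 36 to 45, the probability that the interval lies wholly above 75% ranges over 0.0108 to 0.0284 at 75%, and over 0.0611 to 0.1324 at 87/108. At n = 45 the interval contains 75% for 29 to 39 completions.

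**With the monitoring rules (assumptions needed).**

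- *Feasibility rule (Table 3).* Put each patient in one of three classes from the historical figures: fails 3 cycles (19/108), completes 3 but not 5 (2/108), or completes 5 (87/108). Assume that a patient who misses 3 cycles by 18 weeks also misses 5 by 30 weeks. Then 36 or more completions leave at most 4 failures, and Table 3 (≥ 6/10, ≥ 9/20) cannot be triggered. Overall it triggers with probability 0.0065. The untriggered probabilities are 0.9034 for 25 to 35 completions and 0.0886 for 36 or more.
- *Toxicity rule (Table 5, all three looks: ≥ 4/10, ≥ 5/20, ≥ 7/40).* The exact trigger probability is 0.0005, 0.0057 and 0.1157 at assumed true unacceptable-toxicity rates of 3%, 5% and 10%.

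Assuming toxicity is independent of completion, multiply by the probability of no toxicity trigger:

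| Assumed toxicity rate | Whole rule as written | With upper-limit wording | Gap |
|---|---|---|---|
| 3% | 0.9034 × 0.9995 = 0.903 | 0.9920 × 0.9995 = 0.9915 | 0.0885 |
| 5% | 0.9034 × 0.9943 = 0.898 | 0.9920 × 0.9943 = 0.986 | 0.0881 |
| 10% | 0.9034 × 0.8843 = 0.799 | 0.9920 × 0.8843 = 0.877 | 0.0783 |

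At a true completion rate of 75% the gap is 0.0160, 0.0160 and 0.0142.

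**The case against.** The strongest reply is that nobody would misread the plan. The text says *if*, not *only if*, and all the surrounding text treats low completion as the only failure. Section 9.3.4 has the estimate and its interval reported in any case. A reader who sees 36/40 with an interval of 76.9% to 96.0% would very likely infer feasibility. The gap is also unlikely at the target (1.6%), and the 8.9% borrows a rate from patients who did not receive irinotecan and temozolomide. The error that the study mainly guards against, calling a poor regimen feasible, is unaffected.

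Much of this is right as description. The intent is clear and the gap is not probable at the target. But clear intent shows only that the written condition fails to express the design. A primary decision rule should give an answer for every possible result without relying on the reader to supply it.

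The reply is stronger against the combined figures. Independence of toxicity and completion is doubtful: under Sections 5.2.5.1, 5.2.5.3 and 5.2.5.10, some events on the unacceptable-toxicity list also end protocol therapy, and so count against completion. The choice of looks matters too. At 10% toxicity, Table 5 triggers with probability 0.116 with its final look and 0.047 without it, and Section 9.3.1 speaks of interim rules. At that rate, most of the shortfall from 1 comes from the toxicity rule and not from this gap. Those figures are secondary, and the conclusion does not need them.

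**Conclusion.** The concern holds. As written, the primary rule withholds or omits the feasible conclusion for 36 to 40 completions out of 40, which contradicts the one-directional purpose shown in Sections 9.2, 9.3.1 and 9.3.3.1. That range is exact for n = 40 and rests on no assumption.

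The probability of reaching it, on the interval condition alone, is 1.6% at the 75% target and 8.9% at 87/108, with the latter as a reference only. Allowing for the monitoring rules, under the assumptions above, gives 1.4% to 1.6% and 7.8% to 8.9%.

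This must be fixed because it is the go/no-go rule for the only primary aim, not because the gap is likely to be reached.

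**What to change.** In Sections 9.3.1 and 9.3.4, declare the therapy feasible if the upper limit of the 95% Wilson interval, computed on the actual evaluable number, is at or above 75% and no monitoring rule is triggered. At n = 40 this means 25 or more completions. In Section 9.3.1, describe 0.0769 and 0.4402 as the probability that the upper limit is at or above 75%.

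The cost is one sentence in each of two sections and one reworded probability statement. The sample size, the lower cutoff of 25/40, the monitoring rules and both stated probabilities are unchanged.
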